## 15.2 Sample Size Re-Assessment

To examine whether the variance estimate used in power calculations for the primary endpoint was adequate, an assessment of the variance magnitude will be performed after at least 1/3 of the subjects complete the study treatment period. The EM algorithm of Gould and Shih (Communications in Statistics. A Theory and Methods, 21, 2833-2853, 1992), will be applied to estimate the variance of the change from baseline to Week 12/Treatment Termination in total UPDRS score, without breaking the blind. In the case that the variance estimate will be found to be larger than the one projected, the sponsor reserves the right to up-size the study via protocol amendment.

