### **Sample Size Re-Assessment:**

To examine whether the variance estimate used in power calculations for the primary endpoint was adequate, an assessment of the variance magnitude will be performed after at least 1/3 of the subjects complete the study treatment period. The EM algorithm of Gould and Shih (Communications in Statistics. A Theory and Methods, 21, 2833-2853, 1992), will be applied to estimate the variance of the change from baseline to Week 12/Treatment Termination in total UPDRS score, without breaking the blind. In the case that the variance estimate will be found to be larger than the one projected, the sponsor reserves the right to up-size the study via protocol amendment.

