In animal studies, administering both agents in a slow infusion over 24 hours (mimicking extended-release) further improves their efficacy, presumably by allowing the agents to work together for a longer time, enhancing their mutual action. The half-lives of the currently available pramipexole and rasagiline vary ( $T_{1/2}$  is 8-12 hours for pramipexole, and 1.5-3.5 hours for rasagiline) (Wright CE, 1997) (Thebalut JJ, 2004). Therefore, the P2B001 combination comprises an extended release (ER) profile for both pramipexole and rasagiline, which enables release throughout the day for both drugs, allowing for a longer time of mutual action.

P2B001 is intended to offer a novel approach to PD treatment in that it would be:

- a fixed-dose combination of the two agents;
- an extended-release formulation of both pramipexole and rasagiline; and
- a new low-dose regimen of the two agents intended to maximize efficacy while limiting known adverse effects of approved higher doses of the individual components.

A Phase 2b clinical study (P2B001/001) in patients with early Parkinson's disease testing the low-dose combinations of pramipexole (0.3 or 0.6 mg) and rasagiline (0.75 mg) in an extended-release formulation has recently been completed and demonstrated that the combination provides highly significant and clinically meaningful benefits in comparison to placebo, with a good safety profile (Olanow CW K. K., 2017). The primary efficacy endpoint was the change from baseline to Week 12 in total UPDRS (I+II+III) score. The UPDRS data showed significant improvement at each time point relative to baseline ( $p < 0.0001$  at 4, 8, and 12 weeks) for both the 0.3/0.75 mg and 0.6/0.75 mg dose combinations. The placebo-subtracted differences were statistically significant at 12 weeks, these were -4.67 points for 0.6/0.75 mg ( $p = 0.0004$ ) and -3.84 points for 0.3/0.75 mg ( $p = 0.0027$ ).

Out of the two above tested doses, the 0.6/0.75 mg dose was selected for the phase III study. Although between-group differences in efficacy were not statistically significant, there was consistent numerical benefit for this dose on total, motor and ADL UPDRS scores, PDQ39 and CGI-severity.

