in the combination were either equal (in case of Pramipexole) or lower (in case of Rasagiline) compared to the Cmax and AUC of the drugs given alone, indicating that no safety issues resulting from increased exposure are expected. In this study, the availability of the drugs in the P2B001 is about 90% for pramipexole and about 80% for rasagiline relative to the commercial mono-therapies. Furthermore, both drugs were present in plasma throughout the day and the high peaks associated with the commercial products were avoided with P2B001. The second study has recently been completed. This was a phase 2b, twelve-week multi-center, randomized, double-blind, placebo-controlled, parallel group study, to determine the safety, tolerability and efficacy of two doses of P2B001 in subjects with early Parkinson's disease. The study tested two low-dose, fixed-dose combinations of P2B001, once-daily containing pramipexole and rasagiline (0.6 mg/0.75 mg and 0.3 mg/0.75 mg) relative to an identical placebo capsule. The results demonstrated robust statistically significant and clinically meaningful improvement results compared to placebo in Parkinson's disease symptoms with a favorable safety profile at two dosage strengths of the combination product. The primary efficacy endpoint was the change from baseline to Week 12 in total UPDRS (I+II+III) score. The UPDRS data showed significant improvement at each time point relative to baseline ( $p < 0.0001$  at 4, 8, and 12 weeks) for both the 0.3/0.75 mg and 0.6/0.75 mg dose combinations. The placebo-subtracted differences were statistically significant at 12 weeks, these were -4.67 points for 0.6/0.75 mg ( $p = 0.0004$ ) and -3.84 points for 0.3/0.75 mg (0.0027). Adverse events of frequency  $\geq 5\%$  are listed in the table below.

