## **15.1 Sample Size Rationale**

The study was powered to allow achieving two goals:

- To demonstrate the superiority of P2B001 0.6/0.75mg compared to its individual components in the primary endpoint, the change from baseline to Week 12/Treatment Termination in total UPDRS score:

- The power to meet the primary endpoint was estimated based on simulation runs assuming equal arms size of P2B001 0.6/0.75mg and its individual components as well as repeated UPDRS measurements at baseline, week 4, week 8 and week 12.
- The expected STD of the change from baseline was assumed to be 6.0 UPDRS points.
- The expected treatment effect of P2B001 0.6/0.75mg is 3 UPDRS points over rasagiline 0.75mg and 2.25 UPDRS points over 0.6mg pramipexole.
- Sequential correlations between changes from baseline will be 0.7 and 0.49 between these obtained at week 4 and at week 12.
- Missing observations rate of 10% occurring at random.
- The statistical model used in the simulation study was the Mixed Model for Repeated Measures (MMRM) (SAS® MIXED procedure with REPEATED sub-command) testing two contrasts: P2B001 0.6/0.75mg vs. rasagiline 0.75mg and P2B001 0.6/0.75mg vs. pramipexole 0.6mg at Week 12/Treatment Termination.
- In order to consider the study as successful both tested contrasts have to be statistically significant at 5% two-tailed each.

The simulation indicates that a total of 150 subjects per group treated with P2B001 0.6/0.75mg, rasagiline 0.75mg arm or pramipexole 0.6mg will provide 87.6% power to detect a statistically significant effect size favoring P2B001 0.6/0.75mg by 3 UPDRS points over rasagiline 0.75mg and 2.25 UPDRS points over pramipexole 0.6mg.

- To demonstrate the superiority of P2B001 0.6/0.75mg over pramipexole ER in the first secondary endpoint, namely, the change from baseline to Week 12/Treatment Termination in the ESS:
  - The power to meet this secondary endpoint was estimated using the two-sample t-test for mean difference at a two-sided alpha of 5% (SAS® POWER procedure).
  - The expected STD of the change from baseline was assumed to be 3.0 ESS points.
  - The expected treatment effect of P2B001 0.6/0.75mg over pramipexole ER is 1.5 ESS points.

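### The blinded SD check rests on an EM mixture fit alone, although the planned arm differences are too small for pooled data to separate; the pooled one-sample SD should be used or reported with it

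*Protocol*

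**What the plan says.** Protocol Section 15.2 and the matching synopsis paragraph state that "an assessment of the variance magnitude will be performed after at least 1/3 of the subjects complete the study treatment period". The only estimator named is an EM algorithm, given by literature reference, which "will be applied to estimate the variance of the change from baseline to Week 12/Treatment Termination in total UPDRS score, without breaking the blind". The action rule is: "In the case that the variance estimate will be found to be larger than the one projected, the sponsor reserves the right to up-size". Any increase would be made through a protocol amendment.

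Neither place states the number of mixture components, the weights for the 2:2:2:1 allocation, the starting values, the stopping rule or a second estimator. The SAP addendum does not mention the check. The body of SAP Version 2.0, which takes precedence under Section 15.13, was not supplied.

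The design inputs are in Section 15.1: "The expected treatment effect of P2B001 0.6/0.75mg is 3 UPDRS points over rasagiline 0.75mg and 2.25 UPDRS points over 0.6mg pramipexole", and "The expected STD of the change from baseline was assumed to be 6.0 UPDRS points". With 150 per main arm they give the stated 87.6% power to win both contrasts.

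**The concern.** An EM approach treats the blinded data as a mixture of arms and estimates the within-arm SD by separating them. That needs arm means far enough apart to leave a mark on the pooled distribution. Here they are half an SD apart at most. When the data cannot identify the components, the fit can assign random scatter to spurious arm differences and return a within-arm SD that is too small. How far it goes depends on where it starts and when it stops.

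At stake is the plan's only stated check on the SD behind its power. If that check reads low, a larger SD can pass unnoticed and the option to up-size is not considered.

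**Working it through.** **1. Reproducing 87.6%.** Power per contrast is Φ(δ / (SD·√(2/n)) − 1.96). The joint power is bivariate normal with correlation 0.5, because the P2B001 arm is shared. With SD 6 and effects 3 and 2.25:
- n = 150, no missing data: 89.7%.
- n = 135 (10% lost): 86.2%.
- Repeated-measures information with 10% missing: 87.8% (intermittent) or 87.1% (monotone).

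The stated figure is reproduced. An effective n of 140.6 per arm gives exactly 87.6%: the SE is 6·√(2/140.6) = 0.716, and the contrast powers are 98.7% and 88.2%. At SD 7 the SE is 0.835, and the joint power is 75.0%.

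**2. How separable the arms are.** 2.25/6 = 0.375 SD and 3/6 = 0.5 SD. Assume that pramipexole ER has the P2B001 mean (the documents give none). The relative arm means are 0, 2.25, 3 and 0 with weights 2:2:2:1.
- Overall mean: (2·2.25 + 2·3)/7 = 1.5.
- Between-arm variance: (2·1.5² + 2·0.75² + 2·1.5² + 1.5²)/7 = 12.375/7 = 1.768.
- Pooled SD: √(36 + 1.768) = 6.146.
- Mixture skewness −0.002 and excess kurtosis −0.004. The sampling errors at n = 525/3 = 175 are √(6/175) = 0.19 and √(24/175) = 0.37.

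The mixture cannot be told from a single normal distribution at this size.

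**3. Generic EM fits.** Simulated looks at n = 175; common variance, four components with weights fixed at 2:2:2:1, starts at the planned effects. These settings are assumptions.

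| Estimator | Mean SD, true SD 6 | Reports ≤ 6.0, true SD 7 |
|---|---|---|
| EM, stop at relative SD change 1e-3 | 5.97 | 0.4% |
| EM, 1e-4 | 5.56 | 21% |
| EM, 1e-6 | 5.08 | 50% |
| Pooled one-sample SD | 6.15 (expected) | 0.1% |

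Starting from sample quantiles gives a bias of −21% to −22% at any stop. Across both kinds of start, converged four-component fits miss SD 7 in 54–67% of looks in a larger run, and two-component fits in 32–33%. A second implementation gave means from about 4.9 to 6.1 at true SD 6. At a nominal 1e-3 it averaged 5.56, so even the same quoted tolerance need not give the same result.

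A direct test of information: with identical arms and total SD 6.146, converged four-component fits average 5.12 (planned starts) or 4.72 (quantile starts). With the planned differences they average 5.08 or 4.68. The fit barely responds to whether a difference exists.

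**4. The pooled SD.** 174·s²/SD² is noncentral chi-square with 174 df and noncentrality 175·1.768/SD². At true SD 6, s exceeds 6.0 in 66% of looks, or 49% after subtracting 1.768 from the variance. At true SD 7 it is 6.0 or less in 0.1% (0.5% with subtraction). If the ER mean is 1.5 points worse or better than P2B001, the between-arm variance is 1.40 or 2.69 and the pooled SD at true SD 6 is 6.12 or 6.22.

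**5. Power floors.** Solving the step 1 formula for SD: joint power 85% corresponds to SD 6.22, and 80% to SD 6.62.

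**The case against.** The strongest reply is that the plan's own method has not been tested. It is specified by reference, and neither the cited paper nor the main SAP was available; either may fix the settings. This stands. A reader might infer from the table that the cited algorithm is biased low. The documents do not support that, since every EM figure above comes from assumed weights, starts and stops.

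Some settings also work. Planned-effect starts with a loose stop show essentially no bias and exceed 6.0 in about 49% of looks at true SD 6, which is better calibrated than the unadjusted pooled SD at 66%. This is true, but such a fit stops after about two iterations. It mainly returns its starting point and does not show that the arms were separated.

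Third, the pooled SD with the bare trigger exchanges missed alarms for false ones. At true SD 5.8 it would still exceed 6.0 in about 43% of looks. This stands, so a changed estimator needs a changed trigger as well.

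Finally, SD 7 is an assumed upper case. The phase 2b results ("The placebo-subtracted differences were statistically significant at 12 weeks, these were -4.67 points for 0.6/0.75 mg" with p = 0.0004, and a difference of "3.84 points for 0.3/0.75 mg" with p = 0.0027) back-calculate to about 6.2 to 6.4 using difference / (t·√(1/n₁ + 1/n₂)). That ignores model adjustment, takes group sizes from an adverse-event table and concerns another score: "The primary efficacy endpoint was the change from baseline to Week 12 in total UPDRS (I+II+III) score". At SD 6.3 joint power is still about 84%.

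**Conclusion.** The concern holds as a minor one. On the supplied text, the check relies on one estimator whose result, at the planned separations and about 175 subjects, can depend more on settings than on data. In generic fits the mean at true SD 6 ranges from about 6.0 to about 5.1. A true SD of 7 is missed in about 0% to 50% or more of looks, against about 0.1% or fewer for the pooled SD. This rests on n = 175 (the minimum look), fixed weights, and a pramipexole ER mean equal to that of P2B001.

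A reader might also infer that the trial is underpowered or its error rate compromised. Neither follows. The 87.6% is reproduced under its own assumptions, the look is blinded, the final tests do not change, and up-sizing is at the sponsor's discretion. The harm is confined to a power check that may fail to flag a larger SD.

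**What to change.** In Section 15.2 and the synopsis:

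- Estimate the variance, still blinded, as the one-sample variance of the pooled change in total UPDRS from baseline to Week 12/Treatment Termination. Keep that variable exactly, so that early terminators are handled as now. Use this in place of the EM estimate or, at minimum, report it beside the EM estimate with the EM components, weights, starts and stopping rule stated.
- Re-run the Section 15.1 power calculation with that SD.
- Replace the bare comparison with the projected variance by a joint-power floor that the sponsor fixes before the look. For example, 85% corresponds to an SD of about 6.22 and 80% to about 6.62.
- Optionally subtract the planned between-arm variance (1.77 under the equal-ER assumption).

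The cost is a few sentences and a simpler computation, with the blind kept. The drawback is that the pooled SD is about 2.4% high at SD 6 (6.146/6) and exceeds 6.0 in about 66% of looks when the SD is exactly 6. The floor or the subtraction should therefore accompany it. Subtraction makes the estimate about 2.5% low if the arms do not differ. If the check led to up-sizing, restoring 87.6% would scale with (SD/6)²: about 166 per main arm at SD 6.3 (about 580 in all), or about 204 at SD 7 (about 715).

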### 15.3 Randomization

Randomization will take place following the completion of all screening procedures including subject approval by both site PI and the central EMC.

Up to 525 eligible subjects with early untreated Parkinson's disease (PD) who are not early terminated from the study during screening or baseline visits and are randomized to treatment with P2B001 0.6/0.75 (approximately 150 subjects), or pramipexole 0.6 mg once daily (approximately 150 subjects), or rasagiline 0.75 mg once daily (approximately 150 subjects), or pramipexole ER titrated to therapeutic optimal dose (approximately 75 subjects) using a randomization scheme of 2:2:2:1, respectively.

### 15.4 Data Analyses Sets

The following data analysis sets are defined for this study:

- **Intention-to-Treat Analysis Set (ITT):** The ITT Analysis Set will include all eligible and randomized subjects who are not early terminated from the study during screening or baseline visits according to the treatment group to which they are originally randomized to. The Intention-to-Treat (ITT) analysis set will serve as the principal analysis set for efficacy assessments
- **Modified Intention-to-Treat Analysis Set (mITT):** The mITT Analyses Set is a subset of the ITT Analysis Set including subjects who have at least one post-baseline UPDRS assessment and have taken at least one study drug dose according to the treatment group to which they are originally randomized to.
- **Completers Analysis Set (CO):** The completers analysis set (CO) will consist of all subjects who complete the 12 weeks of the study according to treatment actually administered.
- **Per Protocol Analysis Set (PP):** The per-protocol analysis set (PP) will consist of all subjects included in the CO analysis set without any major protocol violations according to treatment actually administered.
- **Safety Analysis Set (ST):** The safety analysis set (ST) will consist of all subjects who have been randomized and received at least one study drug according to treatment actually administered. The safety analysis set (ST) will serve as the principal analysis set for safety assessments.

### **15.5 Overall Significance Level and Multiplicity Adjustment:**

The overall significance level for this study will be 5% using two-tailed tests. No interim analyses or futility analyses are planned for this study.

The overall, experiment-wise type-I error rate of 5% will be preserved according to the below plan:

1. The principal analysis of the primary endpoint is designed to demonstrate the efficacy of P2B001 0.6/0.75mg as compared to its individual components in the changes from baseline to Week 12/Treatment Termination. Accordingly, analysis will employ two contrasts: P2B001 0.6/0.75mg vs. pramipexole 0.6mg once daily and, P2B001 0.6/0.75mg vs. rasagiline 0.75mg once daily. The type-I error of 5% for multiple contrasts testing for the primary endpoint will be preserved by determining that the primary endpoint is met only if both comparisons will favor P2B001 0.6/0.75mg at a two-tailed alpha level of 5% each.
2. Multiplicity adjustment for multiple endpoints testing for the secondary endpoints will utilize the gate keeping hierarchical method according to the following order and plan:
  - For the 1st secondary endpoint, namely, the P2B001 0.6/0.75mg vs. Pramipexole ER contrast in the change from baseline to Week 12/Treatment Termination in the ESS, will be considered as met only if both primary endpoint contrasts as above defined and the P2B0011 0.6/0.75mg vs. pramipexole ER contrast in the change from baseline to Week 12/Treatment Termination in the ESS will all be met (total of 3 contrasts) at a two-tailed alpha level of 5% each.
  - The 2nd secondary endpoint, namely, the change from baseline to Week 12/Treatment Termination visit in the Total PDQ39 will be considered as met if all of the 3 previous tested contrasts (primary endpoint and 1st secondary endpoint) as well the two contrasts: P2B001 0.6/0.75mg vs. pramipexole 0.6mg once daily and, P2B001 0.6/0.75mg vs. rasagiline 0.75mg once daily in the 2nd secondary endpoint will all be met (total of 5 contrasts) at a two-tailed alpha level of 5% each.
  - The 3rd secondary endpoint, namely, the change from baseline to Week 12/Treatment Termination visit in the ADL UPDRS (part II) score will be considered as met if all of the 5 previous tested contrasts (primary endpoint, 1st and 2nd secondary endpoints) as well the two contrasts: P2B001 0.6/0.75mg vs. Pramipexole 0.6mg once daily and, P2B001 0.6/0.75mg vs. rasagiline 0.75mg once daily in the 3rd secondary endpoint will all be met (total of 7 contrasts) at a two-tailed alpha level of 5% each.
  - The 4th secondary endpoint, namely, the change from baseline to Week 12/Treatment Termination visit in the motor UPDRS (part III) score will be considered as met if all of the 7 previous tested contrasts (primary endpoint, 1st, 2nd and 3rd secondary endpoints) as well the two contrasts: P2B001 0.6/0.75mg vs. Pramipexole 0.6mg once daily and, P2B001 0.6/0.75mg vs. rasagiline 0.75mg once daily in the 4th secondary endpoint will all be met (total of 9 contrasts) at a two-tailed alpha level of 5% each.

- The 5th secondary endpoint, namely, the CGI-S responder's analysis at Week 12/Treatment Termination visit (change from baseline  $\geq 1$  CGI-S points) will be considered as met if all of the 9 previous tested contrasts (primary endpoint, 1st, 2nd, 3rd and 4th secondary endpoints) as well the two contrasts: P2B001 0.6/0.75mg vs. Pramipexole 0.6mg once daily and, P2B001 0.6/0.75mg vs. rasagiline 0.75mg once daily in the 4th secondary endpoint will all be met (total of 11 contrasts) at a two-tailed alpha level of 5% each.

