## 2 SYNOPSIS

Name of Sponsor/Company: Pharma Two B	
Name of Product: P2B001, Pramipexole 0.6 mg /Rasagiline 0.75 mg Once Daily (P2B001 0.6/0.75 mg)	
Name of Active Ingredient: Pramipexole, Rasagiline	
Title of study: A Phase 3, Twelve-week, Multi-Center, Multinational, Randomized, Double-Blind, Double-Dummy, Parallel Group Study to Determine the Efficacy, Safety and Tolerability of P2B001 Once Daily Compared to its Individual Components in Subjects with Early Parkinson's Disease and to a Calibration Arm of Pramipexole ER.	
Study Sites: Approximately 70 sites in the United States, Canada, and Europe will be participating in the study.	
Planned Study Duration 16 – 22 months from first patient in until database lock. Planned first patient in: December 2017	Development Phase: Phase 3
Objectives: Primary objective: To determine the superiority of P2B001 0.6/0.75 mg as compared to its individual components in the change of total UPDRS score (defined as sum of parts II and III, scores (0-160)). Secondary objectives: 

• To determine the superiority of P2B001 0.6/0.75 mg as compared to pramipexole ER in the change of Epworth Sleepiness Scale (ESS) score.

• To determine the efficacy of P2B001 0.6/0.75 mg as compared to its individual components in the change of Total PDQ39 score.

• To determine the efficacy of P2B001 0.6/0.75 mg as compared to its individual components in the change of ADL UPDRS (part II) score.

• To determine the efficacy of P2B001 0.6/0.75 mg as compared to its individual components in the change of motor UPDRS (part III) score.

• To determine the efficacy of P2B001 0.6/0.75 mg as compared to its individual components in the CGI-S responder's analysis (change from baseline <math>\geq 1</math> CGI-S points).

 Exploratory objective:	

- To evaluate the superiority of P2B001 0.6/0.75 mg compared to its individual components in the following endpoints:
  - Change in each of the 8 PDQ39 subscales scores.
  - Change in the score of Health-Related Quality of Life (HRQOL) SF-12v2 questionnaire.
  - Clinical Global Impression of Improvement (CGI-I).
  
- To evaluate the superiority of P2B001 0.6/0.75 mg over pramipexole ER with respect to the following outcome measures:
  - Proportion (%) of patients with ESS score >10.

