### **8.4.2 Clinical Global Impression - severity (CGI-S) - Appendix IV**

This scale will be completed by the Investigator at baseline and at end of week 12/Treatment termination (visit 6). The scale rates the subject's overall well-being, including the Parkinson's

disease symptoms over the week before the visit. The CGI scale refers to the global impression of the subject and requires clinical experience with the syndrome under assessment. The CGI-S scale is a 7-point scale that requires the clinician to rate the severity of the subject's illness at the time of assessment, relative to the clinician's past experience with patients who have the same diagnosis. Considering total clinical experience, a subject is assessed on severity of illness at the time of rating using a nominal scoring system with: 1, normal, not at all ill; 2, borderline ill; 3, mildly ill; 4, moderately ill; 5, markedly ill; 6, severely ill; or 7, extremely ill. Efforts must be made to ensure that the same neurologist performs the CGI-S at all visits.

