#### **15.6.7 Efficacy Endpoints and Analyses**

All efficacy endpoints will be tested for the ITT analysis set controlling for multiplicity as detailed in Section 15.5.

An effort to obtain the efficacy outcome measures data regardless if study treatment was discontinued will be made.

Week 12/Treatment Termination is defined for all statistical analyses involving significance testing as the last visit in which a subject was treated with the study drug.

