**15.6.10.5 CGI-S Responder's Analysis at Week 12/Treatment Termination (change from baseline  $\geq 1$  CGI-S points)**

The 5th secondary endpoint, namely, the CGI-S responder's analysis at Week 12/Treatment Termination (change from baseline  $\geq 1$  CGI-S points) will be considered as met if all of the 9 previous tested contrasts (primary endpoint, 1st, 2nd, 3rd and 4th secondary endpoints) as well the two contrasts: P2B001 0.6/0.75mg vs. pramipexole 0.6mg once daily and, P2B001 0.6/0.75mg vs. rasagiline 0.75mg once daily in the 4th secondary endpoint will all be met (total of 11 contrasts) at a two-tailed alpha level of 5% each.

A subject with an improvement of 1 point or more at Week 12/Treatment Termination as compared to baseline will be classified as a "Responder" while other randomized subjects not falling into this definition will be classified as a "Non-Responders".

The analysis of this binary end-point will be based on estimating 2 contrasts (2 contrasts: P2B001 0.6/0.75mg vs. pramipexole 0.6mg and P2B001 0.6/0.75mg vs. rasagiline 0.75mg) derived from a baseline-adjusted, Logistic Regression model [SAS® PROC GENMOD with DIST=BIN and LINK=LOGIT] to this binary outcome measure. In addition to the treatment group the model will include the following covariates: CGR and baseline CGI-S. The treatment effect (odds-ratios) of P2B001 0.6/0.75mg vs its 2 individual components at Week 12/Treatment Termination on the proportion of responders at Week 12/Treatment Termination and the corresponding adjusted proportions will be displayed. In addition, the number and proportion of responders at Week 12/Treatment Termination will be displayed by treatment group. Exploratory Efficacy Endpoints

Analyses of the exploratory endpoints will provide additional insight into the therapeutic effect of P2B001 0.6/0.75. These endpoints will be tested for the ITT analysis set using the nominal alpha level of 5% without controlling for multiplicity. Detailed statistical methodology to be used for the analyses of these exploratory endpoints will be provided in a more detailed SAP to be developed while the study is ongoing and prior to locking the database and unblinding.

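### The success rule for the fifth secondary endpoint (CGI-S responders) points to the fourth endpoint's contrasts, so as written it contains 9 distinct contrasts, not its stated 11, and none on CGI-S

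*Protocol*

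**What the plan says.** Section 15.6.7 of the protocol makes Section 15.5 the source of the decision rules: "All efficacy endpoints will be tested for the ITT analysis set controlling for multiplicity as detailed in Section 15.5". Section 15.5 then builds a hierarchy in which each step states a cumulative number of contrasts that must all be significant.

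- For the fourth secondary endpoint (motor UPDRS), the clause that adds contrasts ends "in the 4 th secondary endpoint will all be met (total of 9 contrasts) at a two-tailed alpha level of 5% each".
- For the fifth (CGI-S responders), the rule first requires "all of the 9 previous tested contrasts (primary endpoint, 1 st , 2 nd , 3 rd and 4 th secondary endpoints"). It then adds the comparisons of P2B001 with pramipexole 0.6 mg and with rasagiline 0.75 mg "in the 4 th secondary endpoint will all be met (total of 11 contrasts) at a two-tailed alpha level of 5% each".

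The fifth-endpoint rule appears three times with the same wording: in the multiplicity part of the Synopsis (Section 2), in Section 15.5 and in Section 15.6.10.5.

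Section 15.6.10.5 also specifies the CGI-S analysis itself: a logistic regression on responder status with the same two treatment comparisons, in which "the model will include the following covariates: CGR and baseline CGI-S".

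**The concern.** A success rule for a formally controlled endpoint has to include a test of that endpoint. This one does not. Its two added contrasts belong to motor UPDRS, which the same sentence has already counted among the earlier nine.

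Applied literally, the rule is satisfied as soon as the motor UPDRS step is passed, whatever the CGI-S data show. A CGI-S claim made that way would have no error control of its own. If the earlier effects were real and CGI-S had no effect, the chance of a false CGI-S claim would equal the chance of passing the earlier steps, not 5%.

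No other part of the protocol settles the matter, because all three statements of the rule carry the same wording.

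**Working it through.** The check is a count of distinct endpoint-by-comparison pairs. The inputs are the steps of Section 15.5 and the cumulative totals stated there.

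| Step | Endpoint | Contrasts added | Running count | Total stated |
|---|---|---|---|---|
| Primary | Total UPDRS (II+III) | 2 | 2 | both required |
| 1st secondary | ESS, vs pramipexole ER | 1 | 2 + 1 = 3 | 3 |
| 2nd secondary | PDQ39 | 2 | 3 + 2 = 5 | 5 |
| 3rd secondary | ADL UPDRS | 2 | 5 + 2 = 7 | 7 |
| 4th secondary | Motor UPDRS | 2 | 7 + 2 = 9 | 9 |
| 5th secondary, literal | Motor UPDRS again | 0 new | 9 + 0 = 9 | 11 |
| 5th secondary, fifth endpoint named | CGI-S responders | 2 | 9 + 2 = 11 | 11 |

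1. The stated totals of 3, 5, 7 and 9 all reproduce.
2. The total of 11 does not reproduce from the literal text. The rule lists 2 + 1 + 2 + 2 + 2 + 2 = 11 items, but the motor UPDRS pair occurs twice. That leaves 11 − 2 = 9 distinct contrasts, of which none is on CGI-S.
3. If the added clause names the fifth endpoint, the count is 11 distinct contrasts, two of them on CGI-S, which agrees with the stated total.

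Set side by side, the clauses show where the pattern breaks. The PDQ39 step adds contrasts in the second endpoint, the ADL step in the third and the motor step in the fourth, each naming the endpoint it governs. Only the CGI-S step names a different one, and its wording matches that of the motor step above it apart from the total.

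**The case against.** The strongest reply is that this is a cross-reference slip that misleads nobody. The sentence opens by naming the fifth endpoint, calls the other nine contrasts previous ones, and gives a total that is possible only if two CGI-S contrasts are added. Section 15.6.10.5 then specifies exactly those two contrasts. All of that is right. It makes the correction safe, but the rule as printed still does not test its endpoint.

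A second reply is that the protocol may not govern. Sections 2 and 15.13 give the SAP precedence over the protocol. The SAP addendum shows that SAP Version 2.0 names the mITT set as the principal efficacy set, where Section 15.6.7 of the protocol names ITT, so part of the sentence that points to Section 15.5 had already been superseded. This limits what can be claimed. The error is certain for the protocol. Whether it survives in the governing plan cannot be determined here, because SAP Version 2.0 was not available and its addendum deals only with the mITT set.

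A third reply is that nothing quantitative follows for the rest of the trial. That stands too: CGI-S is the last step, so no other test depends on it.

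**Conclusion.** The concern holds. In all three statements of the rule, the CGI-S step contains 9 distinct contrasts against a stated 11, and the two that are missing are the CGI-S contrasts.

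The consequence is limited to the CGI-S claim. Error control for the primary and the first four secondary endpoints, power and sample size are unaffected. The conclusion rests only on the protocol text and a count, with no statistical assumption. It should be fixed because this is the decision rule for a multiplicity-controlled endpoint, although the intended meaning is not in real doubt.

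**What to change.** In the CGI-S rule in the Synopsis, Section 15.5 and Section 15.6.10.5, replace the fourth secondary endpoint by the fifth in the clause that adds the two contrasts. The preceding list of earlier endpoints, which ends with the fourth, is correct and should stay.

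Check the same rule in SAP Version 2.0 first, since it takes precedence. If the slip is there, correct it in a dated addendum before unblinding.

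Optionally, state the direction in the short CGI-S responder label, which speaks only of a change of at least 1 point on a scale that ends at "6, severely ill; or 7, extremely ill". Section 15.6.10.5 already settles the direction ("A subject with an improvement of 1 point or more at Week 12/Treatment Termination as compared to baseline will be classified as"), so this is a clarification and not a second error. The label occurs six times: the Synopsis objectives, the Synopsis multiplicity text, Section 4.2, Section 15.5, and the heading and text of Section 15.6.10.5.

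The cost is one word in three places and one check against the SAP. No analysis, power or sample-size calculation changes. Under Section 17.4, a change to the protocol text needs an amendment approved by the sponsor and each site's ethics committee or review board, so it is sensible to combine it with other changes.
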